2 SYNOPSIS

Sponsor:

AbbVie Inc.

Name of Finished Product: oxybutynin chloride gel

Name of Active Ingredient: oxybutynin chloride

Study Title:

A Two-part, Multicenter, Dose-titration Study Evaluating the Efficacy, Safety, Pharmacodynamics, and Pharmacokinetics of Oxybutynin Chloride 10% Gel for the Treatment of Detrusor Overactivity Associated With a Neurological Condition in Pediatric Patients

Study Number: OG09002

Study Phase: Phase 4

Two-part Study:

This study will be conducted in 2 parts, Pre-Amendment 3 and Post-Amendment 3, as follows:

- Pre-Amendment 3: A double-blind, randomized, placebo-controlled treatment study with open-label extension. Patients will be enrolled into the 6-week placebo-controlled treatment followed by an 8-week open-label treatment phase.
- Post-Amendment 3: An open-label treatment study. Patients will be enrolled in a 6-week open-label treatment phase. A portion of enrolled patients will receive an additional 8 weeks of open-label treatment for a total of 14 weeks of open-label treatment.

Primary Objectives:

The primary objectives are:

- Pre-Amendment 3: To evaluate the efficacy of daily treatment with oxybutynin chloride gel compared to placebo in pediatric patients during the first 6 weeks of a 14-week treatment period.
- Post-amendment 3: To evaluate the efficacy of daily treatment with oxybutynin chloride gel in pediatric patients during the first 6-weeks of a 14-week open-label treatment period.

Secondary Objectives (for Pre-Amendment 3 and Post-Amendment 3):

The secondary objectives are to evaluate the pharmacokinetics, pharmacodynamics, safety, and skin tolerability of *oxybutynin chloride gel* in pediatric patients.

Study Design:

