For patients enrolled under Post-Amendment 3, this will be a multicenter, open-label, dosetitration study in pediatric patients, ages 3 years to < 17 years, who have been diagnosed with detrusor overactivity that is associated with a neurogenic condition. Patients must be suitable candidates for anticholinergic therapy and must be using CIC for bladder control. No changes were made in the starting dose, compared to the Pre-Amendment 3 study design, in that all patients will begin treatment with 0.75 g of gel/day for 2 weeks. Patients will then return to the clinic for a potential dose titration and at this time their dose may be adjusted up to 1 g/day, down to 0.5 g/day, or remain the same at 0.75 g/day, depending on individual response and tolerability. The determination of dose will be based on the investigator's clinical judgment and assessment of the patient's bladder symptoms and treatment side effects. Dose titration will be permitted only once during the entire 14-week treatment period. Patients will continue the adjusted dose for 12 additional weeks until the end of the open-label treatment period. Post-Amendment 3, visits will be identified alphabetically (ie, Visit A through Visit F/ET).

In the Post-Amendment 3 study design (open-label treatment only), the study will consist of a screening period from Day -13 to Day -5 and a 14 week open-label treatment period. The total study duration for each patient will be approximately 16 weeks.

The screening period will include *1* clinic visit; Visit *A* (Screening Visit), where *patients* will be considered for inclusion in the study. Following Visit *A*, all *patients* taking anticholinergic medications will be asked to discontinue treatment and complete a 3-day washout period (*11-day washout period if the patient was previously taking solifenacin*). In addition, *patients* will be

asked to complete a 2-day urinary diary following the washout period and prior to Visit B. To minimize *time* off treatment, *patients* may complete the washout period and urinary diary as close to Visit B as possible.

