9.5.2.4 Visit *E* (Week 10 of Treatment)

Site personnel will perform the following activities at Visit E:

- 1. Perform study treatment accountability.
- 2. Record concomitant medication use.
- 3. Measure and record vital signs (blood pressure, heart rate, respiratory rate, and temperature).
- 4. Query for adverse events.
- 5. Assess erythema/application site adverse events at the most recent application site and document findings.
- 6. Instruct patient/caregiver to complete the anticholinergic questionnaire (Appendix 5) and vision symptom questionnaire (Appendix 6).
- 7. Dispense study treatment kit for the next 4 weeks of treatment.

9.5.2.5 *Visit F* (Week 14 of Treatment) or Early Termination

Visit F will be the end of the open-label treatment period. Patients will undergo evaluation by site personnel who will perform the following activities:

- 1. Collect remaining study treatment and perform study treatment accountability.
- 2. Record concomitant medication use.
- 3. Measure *and record* vital signs (blood pressure, heart rate, respiratory rate, and temperature).
- 4. Query for adverse events.
- 5. Assess erythema/application site adverse events at the most recent application site *and document findings*.
- 6. Instruct patient/caregiver to complete the anticholinergic questionnaire (Appendix 5) *and the vision symptom questionnaire* (Appendix 6).
- 7. Conduct physical examination, which will include a review of the following: body as a whole, skin, HEENT, cardiovascular, respiratory; musculoskeletal, neurologic, lymphatic/thyroid, and abdomen.
- 8. Collect blood and urine samples for laboratory evaluation (Appendix 2).
- 9. Collect urine sample for pregnancy test for all females of childbearing potential (Appendix 2).
- 10. Collect blood sample for PK analysis and record the date and time of collection.

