The *Pre-Amendment 3* PP population will include all *patients* in the *Pre-Amendment 3* ITT population who complete the *double-blind* treatment period of the study and who are without significant protocol violations.

The Post-Amendment 3 PP population will include all patients in the Post-Amendment 3 ITT population who complete the Post-Amendment 3 open-label treatment period of the study and who are without significant protocol violations.

The PK population will include all *patients* who have at least 1 sample draw for plasma concentrations. The PK population will only be used in the summary statistics and analyses of the *PK* data.

Additionally, 2 types of visits are defined for the purposes of analysis and summary:

- Observed cases (OC)
- Last observation carried forward (LOCF)

The OC visits are defined to be those assessment values observed at each scheduled visit. All applicable efficacy and safety variables will be summarized using the OC visits.

The LOCF visit is defined as the last data recorded for each efficacy variable. This visit will be *designated as* Week 6 (LOCF). *The Week 6 (LOCF) visit will be defined for the Post-Amendment 3 open-label period and the Pre-Amendment 3 double-blind period* and will only be used to summarize efficacy data. The LOCF visit provides missing value imputation for *patients* who do not complete the *open-label treatment period (Post-Amendment 3) or the double-blind treatment period (Pre-Amendment 3)* of the study and will include all *patients* in the *corresponding* ITT population.

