candidates for anticholinergic therapy and must be using CIC for bladder control. The study will include a screening period from Day -13 to Day -5 and a 14-week open-label treatment period. The expected duration of the study for each patient will be up to 16 weeks (which includes 2 weeks of screening and 14 weeks of treatment). There are six clinic visits (Visit A – Visit F). No changes were made in the starting dose, compared to the Pre-Amendment 3 study design, in that all participants will begin treatment with 0.75 g of gel/day for 2 weeks. Participants will then return to the clinic for a potential dose titration and at this time their dose may be adjusted up to 1 g/day, down to 0.5 g/day, or remain the same at 0.75 g/day, depending on individual response and tolerability. The determination of dose will be based on the investigator's clinical judgment and assessment of the patient's bladder symptoms and treatment side effects. Dose titration will be permitted only once during the entire 14-week treatment period (at Visit C, Week 2). Participants will continue the adjusted dose for 12 additional weeks until the end of the openlabel treatment period.

[figure not shown]
Safety will be evaluated by monitoring adverse events, physical examinations, vital signs, clinical laboratory evaluations, skin erythema at the application site, and a vision symptom questionnaire.

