Combined Intent-to-Treat (ITT²) (Pre- and Post-Amendment 3)	All participants who receive at least 1 dose of study treatment and have at least one post-baseline value for the primary efficacy variable in the Post-Amendment 3 open-label period and all randomized participants who have at least one post-baseline value for the primary efficacy variable in the Pre-Amendment 3 double-blind period	Actual received or Randomized assignment ³
Post-Amendment 3 Per- Protocol (PP)	All participants in the Post-Amendment 3 ITT population who complete the Post-Amendment 3 open-label treatment period of the study and who are without significant protocol violations	Actual received ¹
Pre-Amendment 3 Per- Protocol (PP)	All participants in the Pre-Amendment 3 ITT population who complete the double-blind treatment period of the study and who are without significant protocol violations	Randomized assignment

- 1 Participants will be summarized according to the study treatment received for majority of the treatment period.
- The primary efficacy variable in the description of each ITT population definition is the change from baseline (CFB) to Week 6 of treatment or the last observation carried forward (LOCF) in the percentage of catheterizations without a leaking accident as recorded in the 2-day urinary diary.
- 3 Actual treatment received for Post-Amendment 3 open-label data and Randomized treatment for Pre-Amendment 3 double-blind treatment period data.

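### The Post-Amendment 3 per-protocol set is tied to completing an open-label period that most of the text runs to Week 14, although its efficacy is analysed at Week 6

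*SAP*

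**What the plan says.** **PP definitions.** SAP Table 5-1 restricts the Post-Amendment 3 PP set to ITT participants "who complete the Post-Amendment 3 open-label treatment period of the study and who are without significant protocol violations". Protocol 11.2 has the same condition: "ITT population who complete the Post-Amendment 3 open-label treatment period of the study and who are without significant protocol violations". The Pre-Amendment 3 PP set instead takes those "who complete the double-blind treatment period of the study and who are without significant protocol violations", which is a 6-week period.

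**Length of the open-label period.** Most of the text gives 14 weeks.
- SAP 4.1 describes a "screening period from Day -13 to Day -5 and a 14-week open-label treatment period".
- Protocol 9.1, after the Week 2 titration visit: "Patients will continue the adjusted dose for 12 additional weeks until the end of the open-label treatment period".
- Protocol 9.5.2.5: "Visit F will be the end of the open-label treatment period". Visit F is Week 14.
- The footnote to SAP Table 5-14 gives Post-Amendment 3 a single, open-label period.

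Two places point to 6 weeks.
- The two-part description in the Protocol synopsis: "Patients will be enrolled in a 6-week open-label treatment phase. A portion of enrolled patients will receive an additional 8 weeks of open-label treatment".
- The LOCF paragraph of Protocol 11.2 explains how Week 6 is filled in for patients who do not complete the "open-label treatment period (Post-Amendment 3) or the double-blind treatment period (Pre-Amendment 3". This treats the two periods as counterparts.

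**When PP efficacy is measured.** Protocol 11.5.3 and SAP 5.1.1.3.1 analyse the PP sets at Week 6 (LOCF) and at observed-case visits. Post-Amendment 3 diaries belong to Visits B and D only (Protocol 9.6.1 and Appendix 1). SAP Table 6-3 defines only Baseline and Week 6 as efficacy visits for this part.

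**The concern.** A PP set should contain the patients who followed the plan up to the point where the endpoint is measured. Here the endpoint is fixed at Week 6, yet on the 14-week reading membership also depends on staying on treatment for 8 further weeks. A child who applied the gel as assigned, returned a valid Week 6 diary, had no violation and stopped at Week 9 would be left out.

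The clause mainly removes children whose outcome is already known. The SAP's Post-Amendment 3 ITT set already requires a post-baseline value of the primary variable, and the only scheduled post-baseline diary is at Visit D.

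Two things follow on this reading. Precision is lost for no gain in adherence up to Week 6. The set is also selected on behaviour after the endpoint: if children who respond poorly or have side effects tend to leave after Week 6, the PP mean change would be biased. The documents do not say why children would stop after Week 6, so bias is possible but not shown. The two PP sets would also use different completion horizons for the same Week 6 endpoint.

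**Working it through.** **Inputs**
- Post-Amendment 3 enrolment: minimum 25 (Protocol 11.1, SAP 5.1.2).
- 14-week completers: about 10 expected (Protocol synopsis, Study Population); at least 10 with 14 weeks of exposure (Protocol 11.1, SAP 5.1.2).
- SD of the change from baseline: 28 (SAP 5.1.2). It was set for the two-arm part, so its use for a one-arm estimate is an assumption.
- Dropout: 10% (same sections, two-arm part). Applying it over 14 weeks is an assumption.

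**The plan's own figure.** No power or precision target is stated for any PP set. The stated power for the two-arm design does reproduce (two-sided alpha 0.05 assumed, noncentral t):
- 48 per arm: noncentrality 20 / (28 × √(2/48)) = 3.50, power 93.4% (stated 93%).
- 43 per arm (48 × 0.9 = 43.2): noncentrality 20 / (28 × √(2/43)) = 3.31, power 90.6% (stated 90%).

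The present point does not depend on these figures.

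**6-week reading.** Everyone who completes Week 6 meets the completion clause. The loss is zero.

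**14-week reading.** Assume all 25 children are evaluable at Week 6.
- Excluded share = 1 − completers/25.
- 95% CI half-width = t(0.975, n−1) × SD/√n. For example, n = 10: 2.262 × 28/√10 = 20.03; n = 25: 2.064 × 28/√25 = 11.56.

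| 14-week completers | Excluded | Half-width, SD 28 | Width relative to n = 25 |
|---|---|---|---|
| 25 | 0% | 11.6 | 1.00 |
| 23 | 8% | 12.1 | 1.05 |
| 22 | 12% | 12.4 | 1.07 |
| 20 | 20% | 13.1 | 1.13 |
| 15 | 40% | 15.5 | 1.34 |
| 10 | 60% | 20.0 | 1.73 |

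The rows for 22 and 23 correspond to 10% dropout (25 × 0.10 = 2.5 lost). The last column does not depend on the SD. With SD 20, the half-width is 8.3 at n = 25 and 14.3 at n = 10; with SD 35, it is 14.5 and 25.0.

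If only 20 children are evaluable at Week 6, then 18, 15 or 10 completers mean 10%, 25% or 50% excluded. The half-widths are 13.9, 15.5 or 20.0, against 13.1 with all 20.

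**The case against.** The strongest reply is that the reach is narrow and the defect depends on one of two readings.

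- **Reach.** The primary analysis uses ITT sets, the secondary endpoints follow it, and the urodynamic endpoints are analysed on ITT only. Protocol 11.5.3 lists PP among additional analyses, and no combined PP set is defined. What is touched is mainly a one-sample PP summary of diary endpoints. This stands, and it limits the weight of the point.
- **Reading.** The synopsis describes a 6-week phase with only some patients continuing, and the LOCF paragraph fits that. The root problem may then be the conflict over period length, with the PP problem as a consequence. This stands in part. But the SAP describes only a 14-week Post-Amendment 3 period, so someone programming from the SAP would apply Week 14. If some children stop at Week 6 by design, that rule drops children who did all that was asked of them.
- **Worst case.** The figure of 10 may be an exposure floor and not a forecast: Protocol 9.2 earlier expected a minimum of 25 extension completers from about 96 enrolled. That is fair, and a range is therefore shown. The worst case does not need the two readings mixed, since the synopsis paragraph on the study population itself pairs a 14-week phase with about 10 expected completers.
- **Convention.** Requiring completion of the assigned period is a recognisable PP rule, and the classification of deviations sits in a separate document (SAP 5.1.1.2.3). It still gives a worse set when the last efficacy measurement comes 8 weeks before the period ends.

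**Conclusion.** The point holds. On the reading that most of the text supports, Post-Amendment 3 PP membership depends on persistence to Week 14 for an endpoint measured at Week 6, unlike the matching Pre-Amendment 3 rule. On the 6-week reading no patient is lost, and what remains is a definition that does not say which period it means.

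The cost on the 14-week reading is small if most children complete: about 5% to 7% wider intervals at 10% dropout. It is large only near 10 completers, where 60% are excluded and the interval is 1.73 times as wide. The absolute half-widths rest on the borrowed SD of 28 and on 25 children being evaluable at Week 6. The width ratios need only the counts. Bias is possible but not demonstrated.

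The ITT-based primary and secondary results do not change. This should be settled before database lock, and it does not threaten the main conclusions.

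**What to change.** In SAP Table 5-1, define the Post-Amendment 3 PP set as ITT participants who complete treatment through Week 6 (Visit D) with no significant protocol violation up to Visit D, parallel to the Pre-Amendment 3 rule. Make the same change in Protocol 11.2 or, if a protocol edit is not wanted, record the departure in SAP 5.2.2.

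Separately, reconcile the synopsis description of a 6-week phase with the passages that give 14 weeks for all patients. The open-label treatment period should have one meaning in both the PP definition and the LOCF paragraph of Protocol 11.2.

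The cost is one sentence in the SAP, one in the protocol if it is amended, and the synopsis wording. No extra data or patients are needed. Doing it before lock also avoids choosing PP membership after results are seen.

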5.1.1.2.4 Demographics and Baseline Characteristics

Demographics and baseline characteristics will be summarized as follows:

- Combined ITT population: double-blind period by treatment group and overall and openlabel periods by oxybutynin chloride gel dose level and overall
- Combined open-label safety population: by oxybutynin chloride gel dose level and overall
- Post-Amendment 3 open-label safety population: by oxybutynin chloride gel dose level and overall

The following demographic and baseline characteristics will be summarized as described below:

Table 5-7 Demographic Summaries

Parameter	Description	Timing	Methodology
Age	Age (years) relative to informed consent date	Informed consent	Continuous descriptives
Age group	 3 to < 6 years 6 to < 12 years 12 to <17 years 	Informed consent	Categorical descriptives
Sex, race, and ethnicity	 eCRF categories Race group White Non-white 	Screening Period	Categorical descriptives
Baseline characteristics	 Height (m) Weight (kg) Body mass index (BMI) Weight (kg) / height (m)² 	Latest assessment in Screening Period	Continuous descriptives
Baseline characteristics	 Age and Weight Category <=18 kg and 3 to < 6 years >18 kg and 3 to < 6 years <=25 kg and 6 to < 12 years >25 kg and 6 to < 12 years <=50 kg and 12 to <17 years >50 kg and 12 to <17 years 	Latest assessment in Screening Period	Categorical descriptives

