5.1.1.4.1 Study Treatment Exposure and Compliance

Study treatment exposure and compliance will be summarized by treatment group or oxybutynin chloride gel level, as applicable, and by visit and overall for each safety population as follows:

Table 5-14 Study Treatment Summaries

Parameter	Description	Timing	Methodology
Study treatment	Date of last dose of the study drug minus Date of	Study Period	Continuous
exposure (days)	first dose of the study drug + 1	within a	descriptives
		Study Part ¹	
Categorical study	Number and percentage of participants exposed	Study Period	Categorical
treatment exposure	to treatment during each of the following	within a	descriptives
	intervals:	Study Part ¹	
	• Week (0, 1]		
	• Week (1, 2]		
	• Week (2, 3]		
	• Week (3, 4]		
	• Week (4, 5]		
	• Week (5, 6]		
	• Week (6, 7]		
	• Week (7, 8]		
	• Week (8, 9]		
	• Week (9, 10]		
	• Week (10, 11]		
	• Week (11, 12]		
	• Week (12, 13]		
	• Week (13, 14]		
	• Week >=14		
Study treatment	Summary by period interval	Study Period	Continuous
compliance (%)	Pre-Amendment 3:	within a	descriptives
	100 × # of sachets dispensed – # returned	Study Part ¹	

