5.1.1.4.2 Adverse Events

Adverse event summaries will be presented for each safety population as follows:

- Post-Amendment 3 open-label safety population: by oxybutynin chloride gel dose level and overall
- Pre-Amendment 3 double-blind safety population: by treatment group, treatment and dose level, and overall
- Pre-Amendment 3 open-label safety population: by oxybutynin chloride gel dose level and overall
- Combined open-label safety population: by oxybutynin chloride gel dose level and overall

Adverse event summaries will be done overall and also for each age, weight, and sex group.

The following adverse event (AE) terms are defined:

An AE will be considered as a treatment-emergent adverse event (TEAE) if the AE initially occurs or increases in intensity on or after the first dose of study drug in the study. An event that occurs more than 30 days after the last dose of study drug will not be considered as treatment-emergent.

Table 5-15 AE Terms

Term	Description
Treatment- emergent	Double-blind period:
emergene	 First dose date of double-blind period ≤ event start date ≤ last dose date of double-blind period + 30 days if participant does not enter the 8-week open-label period; or First dose date of double-blind period ≤ event start date < first dose date of open-label period if participant enters the 8-week open-label period
	 Open-label period: First start date of open-label period ≤ event start date ≤ last dose date of open-label period + 30 days

AEs, encompassing abnormalities and surgeries reported as occurring after the Screening Visit, will be coded using MedDRA Version 19.1 or later. Unique participants reporting AEs in the following AE categories will be summarized for the groups defined above for each safety population as follows:

[figure not shown]

Table 5-16 AE Summaries

Parameter	Description	Timing	Methodology
Overall summary	Overall summary only for the following category: • Treatment-emergent AEs (TEAEs)	Study Period within Study Part ^{2,3} ; Combined open-label period	Categorical descriptives
TEAE	Overall summary and by SOC and PT	Study Period within Study Part ^{2,3} ; Combined open-label period	Categorical descriptives
TEAEs by severity	Overall summary and by SOC, PT, and intensity • Participants categorized overall and within each SOC and PT for the most intense occurrence	Study Period within Study Part ^{2,3} ; Combined open-label period	Categorical descriptives

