TEAE by study treatment relationship	Overall summary and by SOC, PT, and study treatment relationship in descending order	Study Period within Study Part ^{2,3} ; Combined open-label period	Categorical descriptives
Serious TEAEs by study treatment relationship and severity	Overall summary and by SOC, PT, study treatment relationship and intensity • Participants categorized overall and within each SOC and PT for the most intense occurrence	Study Period within Study Part ^{2,3} ; Combined open-label period	Categorical descriptives
TEAEs leading to premature discontinuation ¹	Overall summary and by SOC, PT and study treatment relationship	Study Period within Study Part ^{2,3} ; Combined open-label period	Categorical descriptives

¹ Participants who report ≥ 1 AE in the AE category and all AEs for those participants will be listed. SOCs will be sorted alphabetically; PTs will be sorted in descending frequency in the highest dose group.

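### The by-dose adverse event tables have no rule for which dose an event belongs to; under the labels the SAP does offer, events on 0.75 g that led to a Week 2 reduction would be counted under 0.5 g

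*SAP*

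**What the plan says.** Everyone starts on 0.75 g. After two weeks the investigator may keep the dose, raise it to 1 g or lower it to 0.5 g, judging bladder symptoms and side effects (SAP 4.1). The Pre-Amendment 3 open-label period also started everyone on 0.75 g, with possible adjustment after two weeks (Protocol 9.4.1).

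An event is treatment-emergent if it starts or worsens "on or after the first dose of study drug in the study" (SAP 5.1.1.4.2), up to 30 days after the last dose. Table 5-15 allocates events to the double-blind or open-label period. Nothing allocates an event to the dose being taken at onset.

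The tables are nevertheless split by dose, for example: "Post-Amendment 3 open-label safety population: by oxybutynin chloride gel dose level and overall". The counting unit is the person: "Unique participants reporting AEs in the following AE categories will be summarized for the groups defined above for each safety population". The note under Table 5-16 adds that "PTs will be sorted in descending frequency in the highest dose group".

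Two labels could place a participant in a dose column:

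- Table 5-1 footnote 1, attached to every safety population: "Participants will be summarized according to the study treatment received for majority of the treatment period".
- The titrated dose level, used to describe the gel groups in SAP 5.1.1.1.2 and to distribute the combined open-label safety population in Table 5-4.

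SAP 4 says that table, figure and listing specifications are in a separate document, which was not available for this review.

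**The concern.** The dose after Week 2 depends partly on what happened in Weeks 0-2. A label fixed by the later dose therefore sorts participants by an early outcome and then counts that outcome in the table. A child who has an event on 0.75 g, is reduced and continues on 0.5 g brings the 0.75 g event into the 0.5 g column.

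Safety in children is a secondary objective. Post-Amendment 3 has no comparator, so dose is the only treatment split in its adverse event tables. Those tables are repeated in subgroups: "Adverse event summaries will be done overall and also for each age, weight, and sex group". A reader could conclude that the lowest dose is the worst tolerated when there is no dose effect, or could miss a risk that rises with dose.

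**Working it through.** The plan gives no figure on this point to reproduce. The check first asks where each label sends a Week 0-2 event, then how far the columns could move.

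**Step 1: where the labels send the event.** The share of a completed period spent on the post-titration dose is 12/14 = 86% (Post-Amendment 3), 4/6 = 67% (Pre-Amendment 3 double-blind) and 6/8 = 75% (Pre-Amendment 3 open-label). With T weeks of treatment, the reduced dose is the majority when T - 2 > 2, that is, T > 4.

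| Participant reduced at Week 2 | Majority label | Titrated label | Dose in use at a Week 0-2 event |
|---|---|---|---|
| Treated more than 4 weeks | 0.5 g | 0.5 g | 0.75 g |
| Treated exactly 4 weeks | tie | 0.5 g | 0.75 g |
| Stops before Week 4 | 0.75 g | 0.5 g | 0.75 g |

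So the result for participants who continue does not depend on how footnote 1 is read.

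**Step 2: one worked case.** Only the 10 of 25 with 14 weeks of exposure (SAP 5.1.2) comes from the documents. All else is assumed: first-event risk 5% per week at every dose; exposure 14 weeks in 40%, 6 weeks in 50%, 3 weeks in 10%; chance of reduction 30% with and 10% without a Week 0-2 event; chance of increase 5% and 40%; nobody stops because of an event; majority label.

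- Event in Weeks 0-2: 1 - 0.95² = 0.0975.
- Reduced: 0.0975 × 0.30 + 0.9025 × 0.10 = 0.02925 + 0.09025 = 0.1195.
- Size of the 0.5 g column: 25 × 0.9 × 0.1195 = 2.7 participants.
- Share of that column with an early event on 0.75 g: 0.02925/0.1195 = 24%.
- First event after Week 2, given none before: (0.4/0.9)(1 - 0.95¹²) + (0.5/0.9)(1 - 0.95⁴) = 0.204 + 0.103 = 0.307.
- 0.5 g column: 0.245 + 0.755 × 0.307 = 47.7%.

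The same steps give 34.8% for 0.75 g and 31.7% for 1 g. If titration ignored events, the columns would be 37/33-34/37%.

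**Step 3: range.** Percent of participants with an event in the 0.5/0.75/1 g columns, by chance of reduction with/without an early event. The 80/2 setting is extreme. Stopping means the share of those with a Week 0-2 event who leave before Week 2 and so stay under 0.75 g.

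| Assumption | 30/10 | 50/5 | 80/2 |
|---|---|---|---|
| No dose effect, no stopping | 48/35/32 | 67/33/32 | 87/29/32 |
| No dose effect, 50% stop | 40/37/31 | 55/35/31 | 78/34/31 |
| No dose effect, 80% stop | 35/38/31 | 43/37/31 | 63/36/31 |
| Risk ×1.5 per dose step, no stopping | 41/35/42 | 63/33/42 | 85/30/42 |
| Risk ×1.5 per dose step, 80% stop | 27/38/42 | 36/37/42 | 58/36/42 |

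With the rising risk and titration that ignores events, the columns would be 30/33-34/47. With no dose effect, 0.5 g stops being the highest column once about 69%, 91% or 98% of those with an early event stop. At 30/10 with no stopping and no dose effect, a weekly risk of 2% gives 23/16/14 and 10% gives 71/56/52.

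Expected 0.5 g column sizes without stopping are 2.7, 2.1 and 2.2 of 25, so one participant moves the column by about 37 to 48 points. At 80% stopping they are 2.2, 1.2 and 0.8.

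**Step 4: what dose at onset changes.** Take no dose effect and no stopping. With equal susceptibility, onset attribution gives -ln(0.95) = 5.13 events per 100 patient-weeks at every dose. If susceptibility differs between participants (assumed gamma, mean 1, variance 1), the false 0.5 g to 0.75 g rate ratio in the 30/10 setting is 7.35/5.49 = 1.3 with majority columns and 5.86/5.26 = 1.1 with post-titration onset dose. In the other two settings it falls from 2.4 to 1.4 and from 3.9 to 1.8.

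**The case against.** Footnote 1 may have nothing to do with dose. It hangs on an as-received entry whose counterpart in the same column of Table 5-1 is randomised assignment, which is the usual as-treated versus as-randomised contrast. SAP 5.1.1.1.2 defines the groups as gel or placebo within a period, with doses only in parentheses. This objection stands: the SAP text does not establish that footnote 1 sets the dose columns. It does not remove the problem, because the titrated dose level sends the same participants to 0.5 g.

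The table specifications are unseen and may already use dose at onset. That also stands. What is shown is a gap in the SAP, and that following either of its labels would mislead.

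The tables are descriptive, no objective compares doses, and Protocol 11.6.1 allows the Post-Amendment 3 summary by dose level and/or overall. With so few participants expected on 0.5 g, dose ranking would be fragile under any rule. These points limit the consequence, but the SAP has committed to the by-dose columns.

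The direction is not fixed either. In the mildest setting with rising risk and 80% early stopping, the columns read 27/38/42, which is the right order.

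A reader might extend the point to the questionnaire tables. Those are given by visit and dose level (SAP 5.1.1.5), which fits the dose at the visit equally well. Other tables do use dose as a participant label, such as "Combined open-label safety population: by oxybutynin chloride gel dose level and overall" for demographics, but baseline tables count no events and do not carry this error.

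**Conclusion.** The point holds as a should-fix on the by-dose adverse event tables. Under either label in the SAP, a participant reduced at Week 2 who continues is counted under 0.5 g with the events on 0.75 g behind the reduction, so the tables can misrank the doses. That finding needs no assumed rates. The size and direction do: the illustrative 0.5 g column runs from 27% to 87% at a 5% weekly risk, depending on titration, early stopping and dose effect.

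A reader might infer that the tables will show 0.5 g as the worst tolerated dose, or that the SAP orders dose columns by majority of period. The documents support neither. They give no event, titration or stopping rates, and footnote 1 speaks of study treatment, not dose.

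Overall columns and the randomised gel-placebo comparison are unaffected. Confidence is medium, because the table specifications could settle the matter.

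**What to change.** In SAP 5.1.1.4.2, attribute each treatment-emergent event to the dose in use at onset, or at worsening where that is what makes it treatment-emergent. Add a convention for events that start on the day of a dose change or after the last dose. Show Weeks 0-2 of each period, when all gel participants take 0.75 g, separately from the post-titration period. Use as denominator the number of participants treated at that dose in that interval and, as an addition, patient-weeks at that dose.

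Add exposure by dose and interval to Table 5-14. Exposure is now "summarized by treatment group or oxybutynin chloride gel level, as applicable, and by visit and overall for each safety population" but runs from first to last dose of the period, so it does not give time at each dose. For a participant reduced at Week 2, 2/14 = 14% of a 14-week exposure and 2/6 = 33% of a 6-week exposure was on 0.75 g.

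State whether footnote 1 governs gel versus placebo only. Keep the overall columns, and label by-dose comparisons as descriptive and confounded by titration. If the table specifications already attribute by dose at onset, bring that rule into the SAP.

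The cost is SAP wording and programming. Dosing information is already on the eCRF (Protocol 9.4.2.2), and event start dates are already used in Table 5-15. There are drawbacks:

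- A participant can appear under more than one dose.
- By-dose event denominators will differ from those of other by-dose tables.
- Patient-week rates go beyond the patient-count percentages of Protocol 11.6.1.
- Selection by tolerability remains, so the bias is reduced but not removed.
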